7.1.2. Criteria for Permanent Discontinuation of Study Intervention

In rare instances, it may be necessary for a participant to permanently discontinue (definitive discontinuation) study intervention. If study intervention is definitively discontinued, the participant will be encouraged to remain in the study. See the SoA for data to be collected at the time of discontinuation of study intervention and follow-up and for any further evaluations that need to be completed.

Permanent discontinuation of study intervention should occur if the scenarios described occur during the study.

Participant decision

- The participant requests to discontinue the study intervention.

Investigator decision

- The investigator decides that the participant should be discontinued from the study intervention.

Pregnancy

- The participant becomes pregnant during the study (see Section 8.3.5 and Section 10.4, Appendix 4).

Safety considerations

The participant:

- Has a malignancy (except for successfully treated basal or squamous cell skin carcinoma)
- Answered "yes" to Question 4 or Question 5 on the "Suicidal Ideation" portion of the C-SSRS
- Answered "yes" to any of the suicide-related behaviors on the Suicidal Behavior portion of the C-SSRS
A psychiatrist or appropriately trained professional may assist in the decision to discontinue the participant.
- Is diagnosed with LTBI during the study and are not a candidate for treatment as described in Section 7.1.1.1, or
- Has a serious or opportunistic infection that in the opinion of the investigator merits the study intervention being discontinued. Such infections may include, but are not limited to:
 - HIV/acquired immune deficiency syndrome (AIDS) infection
 - active TB infection or untreated LTBI (see Sections 7.1.1 and 8.2.6)
 - HCV RNA positive (Section 8.2.8)
 - HBV DNA positive (Section 8.2.7).

The participant should be referred to, evaluated and managed by a specialist physician with expertise in evaluation and management of viral hepatitis prior to discontinuation of any

immunomodulatory and/or immunosuppressive therapy, including study intervention. Timing of discontinuation from study intervention relative to the initiation of any antiviral treatment for hepatitis is to be based on the recommendation of the consulting specialist physician, in conjunction with the investigator, and aligned with medical guidelines and standard of care.

Hepatic event or liver test abnormality

Participants who are discontinued from intervention due to a hepatic event or liver test abnormality should have additional hepatic safety data collected via eCRF. The investigator should consult with the medical monitor to determine if discontinuation of the intervention for abnormal liver tests **should be** considered if a participant meets one of these conditions (see Section 10.7, Appendix 8):

- ALT or AST >8 times ULN
- ALT or AST >5 times ULN for more than 2 weeks
- ALT or AST >3 times ULN and TBL >2 times ULN or international normalized ratio (INR) >1.5
- ALT or AST >3 times ULN with the appearance of fatigue, nausea, vomiting, right upper-quadrant pain or tenderness, fever, rash, and/or eosinophilia (>5%)
- ALP >3 times ULN
- ALP >2.5 times ULN and TBL >2 times ULN, or
- ALP >2.5 times ULN with the appearance of fatigue, nausea, vomiting, right quadrant pain or tenderness, fever, rash, and/or eosinophilia (>5%)

See the SoA for data to be collected at the time of intervention discontinuation and follow-up and for any further evaluations that need to be completed.

7.2. Participant Discontinuation/Withdrawal from the Study

A participant may withdraw from the study:

- at any time at his/her own request
- at the request of his/her designee (for example, legal guardian)
- at the discretion of the investigator for safety, behavioral, compliance, or administrative reasons
- if the participant becomes pregnant during the study
- if enrollment in any other clinical study involving an investigational product or enrollment in any other type of medical research judged not to be scientifically or medically compatible with this study
- if the participant, for any reason, requires treatment with another therapeutic agent that has been demonstrated to be effective for treatment of the study indication, discontinuation from the study occurs prior to introduction of the new agent

Discontinuation is expected to be uncommon.

At the time of discontinuing from the study, if possible, an early discontinuation visit should be conducted, as shown in the SoA. See SoA (Section 1.3) for data to be collected at the time of study discontinuation and follow-up and for any further evaluations that need to be completed. The participant will be permanently discontinued from the study intervention.

If the participant withdraws consent for disclosure of future information, the sponsor may retain and continue to use any data collected before such a withdrawal of consent. If a participant withdraws from the study, he/she may request destruction of any samples taken and not tested, and the investigator must document this in the site study records.

7.2.1. Discontinuation of Inadvertently Enrolled Participants

If the sponsor or investigator identify a participant who did not meet enrollment criteria and was inadvertently enrolled, then the participant should be discontinued from study treatment unless there are extenuating circumstances that make it medically necessary for the participant to continue on study treatment. Additional country-specific requirements for discontinuation of inadvertently enrolled participants is provided in Section 10.10, Appendix 10.

The investigator should consult with the Medical Monitor, then determine if it is medically appropriate to continue. The investigator must obtain documented approval from the Medical Monitor to allow the inadvertently enrolled participant to continue in the study with or without treatment with investigational product.

Safety follow up is as outlined in:

- Section 1.3 (SoA)
- Section 8.2 (Safety Assessments), and
- Section 8.3 (Adverse Events and Serious Adverse Events).

7.3. Lost to Follow up

A participant will be considered lost to follow-up if he or she repeatedly fails to return for scheduled visits and is unable to be contacted by the study site. Site personnel are expected to make diligent attempts to contact participants who fail to return for a scheduled visit or were otherwise unable to be followed up by the site.

Site personnel, or an independent third party, will attempt to collect the vital status of the participant within legal and ethical boundaries for all participants randomized, including those who did not get study intervention. Public sources may be searched for vital status information. If vital status is determined to be deceased, this will be documented and the participant will not be considered lost to follow-up. Sponsor personnel will not be involved in any attempts to collect vital status information.

Discontinuation of specific sites or of the study as a whole are handled as part of Section 10.1, Appendix 1.

8. Study Assessments and Procedures

Study procedures and their timing are summarized in the SoA. Protocol waivers or exemptions are not allowed.

Immediate safety concerns should be discussed with the sponsor immediately upon occurrence or awareness to determine if the participant should continue or discontinue study intervention.

Adherence to the study design requirements, including those specified in the SoA, is essential and required for study conduct.

All screening evaluations must be completed and reviewed to confirm that potential participants meet all eligibility criteria. The investigator will maintain a screening log to record details of all participants screened and to confirm eligibility or record reasons for screening failure, as applicable.

Monitoring of blinded safety data will continue throughout the study and will be conducted by blinded study team members. Details of the blinded safety reviews, including the frequency and approximate timing, are specified in the trial level safety review plan.

8.1. Efficacy Assessments

All patient-reported and clinician-reported efficacy assessments will be captured on an electronic tablet collected at site visits.

8.1.1. Disease Activity Score—High-Sensitivity C-Reactive Protein (DAS28-hsCRP)

The DAS28-hsCRP measures disease activity in 28 joints using a composite numeric score of the following variables (Vander Cruyssen et al. 2005):

- TJC (see Section 8.1.4)
- SJC (see Section 8.1.4)
- high sensitivity C-reactive protein (hsCRP), and
- Patient's Global Assessment of Disease Activity (PaGADA_VAS; see Section 8.1.7).

The 28 joints examined and assessed as tender or not tender for TJC and as swollen or not swollen for SJC include 14 joints on each side of the participant's body (Smolen et al. 1995):

- the 2 shoulders
- the 2 elbows
- the 2 wrists
- the 10 metacarpophalangeal joints
- the 2 interphalangeal joints of the thumb
- the 8 proximal interphalangeal joints, and
- the 2 knees.

8.1.2. Disease Activity Score—Erythrocyte Sedimentation Rate (DAS28-ESR)

The DAS28-ESR measures disease activity in 28 joints using a composite numeric score of the following variables (Vander Cruyssen et al. 2005):

- TJC (Section 8.1.4)
- SJC (Section 8.1.4)
- Erythrocyte sedimentation rate (ESR), and
- PaGADA_VAS (Section 8.1.7).

For description of the 28 joints to be examined, see Section 8.1.1.

The DAS28-ESR remission is defined as DAS28-ESR <2.6 , and DAS28-ESR LDA is defined as DAS28-ESR ≤ 3.2 .

8.1.3. American College of Rheumatology Criteria (ACR20, ACR50, and ACR70)

The ACR20 is defined as at least 20% improvement in the ACR core set values. Similarly, ACR50 and ACR70 are defined as at least 50% and 70% improvement in the ACR core set values.

This is defined as:

- an improvement of at least 20%, 50%, or 70% in the TJC and SJC (68/66; Section 8.1.4) AND
- an improvement of at least 20%, 50%, or 70% in at least 3 of the following 5 assessments:
 1. Patient's Global Assessment of Arthritis Pain (visual analog scale [VAS]; Section 8.1.6)
 2. PaGADA_VAS (Section 8.1.7)
 3. PhGADA_VAS (Section 8.1.5)
 4. Patient's Assessment of Physical Function as measured by the Health Assessment Questionnaire-Disability Index (HAQ-DI; Section 8.1.8)
 5. Acute phase reactant as measured by hsCRP

8.1.4. Tender Joint Count and Swollen Joint Count

The joint exam will be performed by the Joint Assessor and reviewed by the Safety Assessor (Section 6.3).

8.1.5. Physician's Global Assessment of Disease Activity (PhGADA_VAS)

The PhGADA_VAS is used as a component of ACR (Section 8.1.3) as well as a separate efficacy assessment.

The PhGADA_VAS is a single item that asks the physician to assess the patient's current disease activity on a 0- to 100-mm VAS, with anchors of 0 = "no disease activity" and 100 = "extremely active disease."

8.1.6. Patient's Global Assessment of Arthritis Pain (Visual Analog Scale)

The Patient's Global Assessment of Arthritis Pain (VAS) is used as a component of ACR (Section 8.1.3) as well as a separate efficacy assessment.

The Patient's Global Assessment of Arthritis Pain (VAS) is a single item that asks the patient to rate the current severity of their pain in relation to their RA on a 0- to 100-mm VAS, with anchors of "no pain" and "worst possible pain."

8.1.7. Patient's Global Assessment of Disease Activity (PaGADA_VAS)

The PaGADA_VAS is used as a component of ACR (Section 8.1.3) as well as a separate efficacy assessment.

The PaGADA_VAS is a single item that asks the patients to indicate how they feel their RA is today on a 0- to 100-mm VAS, with anchors of 0 = "very well" and 100 = "very poor."

8.1.8. Health Assessment Questionnaire - Disability Index (HAQ-DI)

The HAQ-DI is used as a component of ACR (Section 8.1.3) as well as a separate efficacy assessment.

The HAQ-DI is a patient-reported questionnaire that is commonly used in RA to measure disease-associated disability (assessment of physical function). It consists of 24 questions referring to 8 domains (Fries et al. 1980, 1982; Ramey et al. 1996):

1. dressing/grooming
2. arising
3. eating
4. walking
5. hygiene
6. reach
7. grip, and
8. activities.

Participants use a scale from 0 to 3 to score difficulty when performing these and other daily activities over the past week (0 = without any difficulty, 1 = with some difficulty, 2 = with much difficulty, and 3 = unable to do). The reported use of special aids or devices and/or the need for assistance of another person to perform these activities is also assessed. Higher scores indicate more limitations in physical function. The scores for each of the functional domains will be averaged to calculate the functional disability index.

8.1.9. Simplified Disease Activity Index (SDAI)

The SDAI is a tool for measurement of disease activity in RA that integrates measures of physical examination, acute phase response, patient self-assessment, and evaluator assessment. The SDAI is calculated by adding together scores from the following assessments:

- number of swollen joints (0 to 28)
- number of tender joints (0 to 28)
- CRP in mg/dL (0.1 to 10.0)
- PaGADA_VAS (0 to 100 mm), and
- PhGADA_VAS (0 to 100 mm) (Aletaha and Smolen 2005).

Disease remission according to ACR/EULAR index-based definition of remission is defined as an SDAI score of ≤ 3.3 (Felson et al. 2011). Low disease activity is defined as an SDAI score of ≤ 11 .

8.1.10. Clinical Disease Activity Index (CDAI)

The CDAI is similar to the SDAI, but it allows for immediate scoring because it does not use a laboratory result. The CDAI is calculated by adding together scores from the following assessments:

- number of swollen joints (0 to 28)
- number of tender joints (0 to 28)
- PaGADA_VAS (0 to 100 mm), and
- PhGADA_VAS (0 to 100 mm) (Aletaha and Smolen 2005).

Remission is defined as a CDAI score of ≤ 2.8 (Felson et al. 2011). Low disease activity is defined as a CDAI score of ≤ 10 .

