4.4.1.2.6 SDAI

The SDAI is calculated by adding together scores from the following assessments:

- number of swollen joints (0 to 28)
- number of tender joints (0 to 28)
- CRP in mg/dL (0.1 to 10.0)

- PaGADA_VAS (0 to 100 mm), and
- PhGADA_VAS (0 to 100 mm) (Aletaha and Smolen 2005).

Observed values at baseline and changes from baseline to Week 12 endpoint in SDAI score will be summarized by treatment arm and provided as listing. An MMRM model, as described in Section 4.3.2, will be used to test the treatment difference of each LY dose versus placebo in change from baseline to Week 12 endpoint.

For participants who discontinue study intervention and/or receive rescue therapy, post-discontinuation or post-rescue observations will not be included.

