4.4.1.2.7 CDAI

The CDAI is calculated by adding together scores from the following assessments:

- number of swollen joints (0 to 28)
- number of tender joints (0 to 28)
- PaGADA_VAS (0 to 100 mm), and
- PhGADA_VAS (0 to 100 mm) (Aletaha and Smolen 2005).

Observed values at baseline and changes from baseline to Week 12 endpoint in CDAI score will be summarized by treatment arm and provided as listing. An MMRM model, as described in Section 4.3.2, will be used to test the treatment difference of each LY dose versus placebo in change from baseline to Week 12 endpoint.

For participants who discontinue study intervention and/or receive rescue therapy, post-discontinuation or post-rescue observations will not be included.

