4.5.4 CDAI Remission and Low Disease Activity

Remission is defined as a CDAI score of ≤ 2.8 . Low disease activity is defined as a CDAI score of ≤ 10 .

The frequency and percentage of patients achieving remission and low disease activity will be summarized by treatment arm at each post-baseline visit. A logistic regression model will be used to test the treatment difference of each LY dose versus placebo at each post-baseline visit with treatment group, baseline value, and previous RA therapy population as model covariates. NRI as described in Section 4.1 will be used to impute missing data for CDAI remission and low disease activity in patients who were Week 12 non-responders or who discontinued prior to Week 12.

The analyses for CDAI remission and CDAI LDA will be repeated for all visits in period 2. NRI as described in Section 4.1 will be used to impute missing data for CDAI in patients who were Week 24 non-responders or who discontinued prior to Week 24.

For participants who discontinue study intervention and/or receive rescue therapy, post-discontinuation or post-rescue observations will not be included.

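### CDAI and SDAI add two 0–100 mm VAS without rescaling, so the low-disease-activity and remission cut-offs, and the Week 14 dosing rule, are almost unreachable as written

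*Protocol*

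**What the plan says.** Protocol 8.1.10 lists four CDAI components: swollen joints (0 to 28), tender joints (0 to 28), the patient global, given as "PaGADA_VAS (0 to 100 mm", and the physician global on the same range. Protocol 8.1.9 uses the same four for SDAI and adds CRP in mg/dL (0.1 to 10.0). The SAP states the operation in sections 4.4.1.2.7 ("The CDAI is calculated by adding together scores from the following assessments") and 4.4.1.2.6 ("The SDAI is calculated by adding together scores from the following assessments"), with the same components and ranges.

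The instrument sections agree on units. Protocol 8.1.7 asks patients "how they feel their RA is today on a 0- to 100-mm VAS", and 8.1.5 asks the physician to rate "current disease activity on a 0- to 100-mm VAS". Neither document divides a VAS by 10 or uses centimetres.

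The cut-offs applied to these sums are:

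- CDAI: "Low disease activity is defined as a CDAI score of ≤ 10" (Protocol 8.1.10) and "Remission is defined as a CDAI score of ≤ 2.8" (SAP 4.5.4).
- SDAI: "Low disease activity is defined as an SDAI score of ≤ 11" (Protocol 8.1.9), with remission at 3.3 or below (Protocol 8.1.9, SAP 4.5.3).

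Protocol 1.1, 4.1 and 6.5.3 then use CDAI of 10 or below at Week 14 to decide who stays on LY3462817. A participant on active drug who misses it stops infusions and moves to standard of care.

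**The concern.** The scale of the sum and the size of the cut-offs do not fit each other. If each global can contribute up to 100 points, a threshold of 10 on the total leaves no practical room for either global, even when every joint is quiet. The cut-offs look as if they belong to a sum in which each global contributes at most 10.

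Three things depend on this:

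- **Dosing.** The Week 14 rule removes participants from LY3462817. Protocol 8.1.10 notes that CDAI can be scored on the spot because it needs no laboratory value, so hand calculation from the protocol text at a visit is realistic. The group meant to supply Period 2 safety and efficacy data comes from about 60 participants randomized to active drug (40 + 20), and literal scoring would deplete it.
- **Responder endpoints.** The four SDAI/CDAI remission and low-disease-activity endpoints at Week 12 (Protocol 9.4.4) and the SDAI/CDAI parts of the two durability endpoints (Protocol 3) would be misclassified.
- **Change scores.** The secondary SDAI and CDAI changes from baseline would be driven mainly by the two VAS.

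**Working it through.** The plan gives no figure of its own to reproduce here. The check is arithmetic on the stated rule, compared with the same rule when each VAS is divided by 10. All inputs are the ranges and cut-offs in Protocol 8.1.9 and 8.1.10.

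**1. Range of each index and the share supplied by the VAS**

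- CDAI as written: 28 + 28 + 100 + 100 = 256; VAS share 200/256 = 78%.
- CDAI with mm/10: 28 + 28 + 10 + 10 = 76; VAS share 20/76 = 26%.
- SDAI as written: 256 + 10 = 266; VAS share 200/266 = 75%.
- SDAI with mm/10: 76 + 10 = 86; VAS share 20/86 = 23%.

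**2. What the cut-offs allow when there are no tender or swollen joints**

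For CDAI, the two globals together may total the cut-off itself as written, or ten times the cut-off with mm/10. For SDAI, the CRP floor of 0.1 mg/dL is subtracted first.

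| Criterion | Allowed sum of both globals, as written | With mm/10 |
|---|---|---|
| CDAI ≤ 10 | 10 mm of 200 (5%) | 100 mm of 200 (50%) |
| CDAI ≤ 2.8 | 2.8 mm of 200 (1.4%) | 28 mm of 200 (14%) |
| SDAI ≤ 11 | 11 − 0.1 = 10.9 mm | 109 mm |
| SDAI ≤ 3.3 | 3.3 − 0.1 = 3.2 mm | 32 mm |

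**3. Individual CDAI scores**

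- No active joints, both globals 6 mm: 0 + 0 + 6 + 6 = 12, which misses low disease activity. With mm/10 the score is 1.2.
- One swollen and one tender joint, globals 20 and 15 mm: 1 + 1 + 20 + 15 = 37. With mm/10 it is 5.5.
- Two swollen and two tender joints, both globals 15 mm: 2 + 2 + 15 + 15 = 34. With mm/10 it is 7.0.

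**4. Improvement needed to meet the Week 14 rule (assumed baselines)**

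The documents give no baseline values. Assume swollen and tender 28-joint counts of 6 to 15 each and each VAS at 40 to 70 mm.

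- As written, baseline CDAI runs from 2×6 + 2×40 = 92 to 2×15 + 2×70 = 170. Reaching 10 needs a fall of 1 − 10/92 = 89% to 1 − 10/170 = 94%. A uniform 70% improvement leaves 0.3×92 = 28 to 0.3×170 = 51, a miss throughout.
- With mm/10, baseline runs from 12 + 8 = 20 to 30 + 14 = 44. The fall needed is 50% to 77%, and a 70% improvement leaves 6.0 to 13.2.

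**5. Illustrative simulation (all distributions assumed)**

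Sixteen settings were run with 400,000 participants each: negative-binomial joint counts, beta-distributed VAS, four sets of means, VAS SD 12 or 22 mm, and latent correlation 0.3 or 0.6. The share with CDAI ≤ 10 was 0% to 52% as written and 13% to 90% with mm/10, lower as written by 13 to 70 percentage points. The direction is certain, because dividing a non-negative VAS by 10 can only lower the score. Only the size is informative, and it depends on the assumptions.

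**The case against.** The strongest reply has four parts.

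- **Which scale the cut-offs belong to.** Neither document says; that lies in cited publications not available here. This stands as a limit on what can be said about intent, and it is why the sponsor is asked to confirm. It does not make the literal rule workable.
- **The millimetre range may only describe what is collected.** The protocol also leaves out the DAS28-CRP formula, so it does not spell out every algorithm. This reading fails because both documents state the operation: the listed scores are added together. The plan does specify units and scale adjustments elsewhere. SDAI fixes the CRP unit, and SAP 4.5.5 multiplies synovitis by 3 and cartilage loss by 2.5 to balance unequal scales.
- **Harm depends on literal use.** The electronic tablet or the scoring program may already rescale, and neither document says who computes the Week 14 CDAI. This stands: the harm is conditional. But Protocol section 8 requires adherence and bars waivers, so the text has to be right.
- **Reach is limited.** The responder and durability endpoints are exploratory, the secondary change scores carry no power claim, and both can be recomputed from stored VAS data. The Week 14 decision falls after the primary endpoint, and all placebo participants go to standard of care regardless. This also stands, apart from the Week 14 stop, which cannot be reversed by recomputation.

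The simulation deserves little weight. Some inputs are implausible: a beta VAS with mean 10 mm and SD 22 mm puts about 65% of participants below 1 mm, and that setting produces the 52% figure.

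**Conclusion.** The concern holds. As written, the scoring rule and its cut-offs are incompatible, and a participant with no active joints can be classed as outside low disease activity and taken off LY3462817. The tenfold difference in what the two globals may contribute follows from the documents' own ranges and needs no outside source or distributional assumption.

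Two things are inferred: that the intended scale is 0–10, and that someone would apply the text literally. The case for correcting the rule rests mainly on the Week 14 decision. The effect on SDAI/CDAI endpoints is real but recoverable. The primary DAS28-CRP comparison, its power and the DAS28-based measures do not change.

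**What to change.** In Protocol 8.1.9 and 8.1.10 and SAP 4.4.1.2.6 and 4.4.1.2.7, state that each global enters the sum as its VAS in mm divided by 10, giving a 0 to 10 contribution. The sponsor should confirm that this is the intended scale. In Protocol 8.1.10, add that the Week 14 CDAI used for continuation in 1.1, 4.1 and 6.5.3 is calculated the same way. Then check the scoring program and how sites obtain the Week 14 value.

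The cost is a short clarification of both documents. The protocol change should go to the IRB/IEC under 10.1.1, because the rule governs dosing. No new data are needed, since both VAS are already collected. If the systems already rescale, the change only makes the text accurate.
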